7.4.3. Analysis of the primary efficacy endpoint and key secondary efficacy endpoints

Label of estimand	Description of estimand	Main estimator			Sensitivity/ Supplementary analysis
		Analysis sets	Rules for imputation	Model/method for the main analytical methods	
Estimand of primary endpoint	
The difference in efficacy in patients aged 12 years and older with moderate to severe AD and weighing > 40 kg between the CBP-201 300 mg Q2W group and placebo group.
 
A patient is considered as treatment success if the patient has an IGA score of 0-1 which is decreased by ≥ 2 points from baseline at W16.
 
A patient should be regarded as treatment failure if he/she uses prohibited drugs/treatments specified in the protocol for which the study treatment must be early terminated or other rescue therapy that has a major impact on the assessment of the primary endpoint due to poor response, or has premature discontinuation of treatment/EOT due to AEs.
	FAS1 (will include all subjects in RS1 who have received the study drug at least once).	
For subjects who experience intercurrent events, their visits after the intercurrent events will be handled in accordance with the strategies for managing intercurrent events listed in Table 7.4.2.
 
If the target variable is still missing after application of the strategies for managing intercurrent events, the multiple imputation (MI) method will be used to impute the missing data in the placebo group, and the J2R (jump to reference) method will be used to impute the missing data in the CBP- 201 group.
	
Differences in response rates between the treatment group and placebo group and their 95% confidence intervals will be analyzed using the Cochran-Mantel-Haenszel test stratified by baseline disease severity (IGA 3 or 4). The Type I error level for statistical significance of the difference in response rates between CBP-201 and placebo is set at 0.05 (two-sided test).
	
Sensitivity analysis 1: When the target variable is still missing after application of the strategy for managing intercurrent events, it will be classified as treatment failure.
 
Sensitivity analysis 2: When the target variable is still missing after application of the strategy for managing intercurrent events, tipping point analysis will be used for analysis.
 
Sensitivity analysis 3: For the subjects who are incorrectly stratified and randomized, the analysis will be performed using the stratification during randomization and the same method as the main estimand;
 
Supplementary analysis 1: The analysis will be performed using the same method as the main estimand based on the PPS1.
 
Supplementary analysis 2: The treatment policy strategy will be used for all intercurrent events; the FAS1 will be used,

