Estimand of key secondary endpoints	
The differences in the following measures in patients aged 12 years and older with moderate to severe AD and weighing ≥ 40 kg between the CBP-201 300mg Q2W group and the placebo group:
 
 • The proportion of subjects achieving EASI-75 at W16 • The proportion of subjects whose weekly average PP-NRS is decreased by ≥ 4 points from baseline at W16; • The proportion of subjects whose weekly average PP-NRS is decreased by ≥ 3 points from baseline at W16; 	FAS1 (will include all subjects in RS1 who have received the study drug at least once).	
For subjects who experience intercurrent events, their visits after the intercurrent events will be handled in accordance with the strategies for managing intercurrent events listed in Table 7.4.2.
 
If the target variable is still missing after application of the strategies for managing intercurrent events, the multiple imputation (MI) method will be used to impute the missing data in the placebo group, and the J2R (jump to reference)
	
For categorical variables, differences in response rates between the treatment group and placebo group and their 95% confidence intervals will be analyzed using the Cochran-Mantel-Haenszel test stratified by baseline disease severity (IGA 3 or 4).
 
For continuous variables, analysis will be performed using an MMRM model that will include treatment group, baseline disease severity (IGA 3 or 4), baseline value of the
	
Sensitivity analysis 1: When the target variable is still missing after application of the strategy for managing intercurrent events, categorical variables will be classified as treatment failure. Continuous variables should be imputed with WOCF.
 
Sensitivity analysis 2: For the subjects who are incorrectly stratified and randomized, the analysis will be performed using the stratification during randomization and the method the same as the main estimator;
 
Supplementary analysis 1: The analysis will be performed using the same method as the main estimand based on the PPS1.
 
Supplementary analysis 2: The treatment policy strategy will be used for all intercurrent events; the FAS1 will be used,

Label of estimand	Description of estimand	Main estimator			Sensitivity/ Supplementary analysis
		Analysis sets	Rules for imputation	Model/method for the main analytical methods	

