	
 Change and percentage change in the weekly average PP-NRS from baseline at W16; The proportion of subjects achieving EASI-90 at W16 
A patient should be regarded as treatment failure if he/she uses prohibited drugs/treatments specified in the protocol for which the study treatment must be early terminated or other rescue therapy that has a major impact on the assessment of the key secondary endpoints due to poor response, or has premature discontinuation of treatment/EOT due to AEs. In this case, continuous variables should be imputed with WOCF.
		method will be used to impute the missing data in the CBP- 201 group.	corresponding endpoint, visit, interaction of visit and treatment group, and the LSMEAN estimate values and their 95% confidence intervals will be summarized.	and the missing data will be subject to the imputation rules of the main estimator, that is, the multiple imputation method (MI) will be used to impute the missing data in the placebo group, and the J2R (jump to reference) method will be used to impute the missing data in the test group.

In the J2R (jump to reference) method, when the data of subjects of the active treatment group are missing, it is assumed that their statistical results are the same as those of the placebo group, that is, it is considered that the pharmacological action of the drug for the active treatment group is the same as that of the placebo group. PROC MI will be used for J2R imputation, and the missing data of the active treatment group will be imputed with the results obtained by posterior predictive distribution of the placebo group. Markov Chain Monte Carlo (MCMC) will be used to extend the data, and a regression method will be used to generate M datasets (M is set as 30 for the primary analysis and as 1000 for other cases in this study). The imputed variables should include: treatment group, stratification factor (severity of baseline disease), baseline value of corresponding endpoint and measurement at each visit. Random seed is the earliest date of the first dose to all subjects.

Table 5 Random Seeds of Multiple Imputation

Endpoints	Random Seeds
IGA	Minimum date of the first dose
EASI	Minimum date of the first dose + 1
PP-NRS	Minimum date of the first dose + 2
BSA	Minimum date of the first dose + 3
SCORAD	Minimum date of the first dose + 4
DLQI	Minimum date of the first dose + 5
POEM	Minimum date of the first dose + 6

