Tipping point analysis: To evaluate the robustness of the primary efficacy endpoint analysis, tipping point analysis should be performed on the primary efficacy endpoint at W16. The tipping point method is binary, that is, the assumptions of missing values of the active treatment group and the placebo group are mutually independent. Assuming that the response rate of missing values of the two groups increases by 10% from 0 to 100%, the subjects with a missing response in the two groups at a certain percentage will be randomly assigned as responders and non-responders in a specified number of imputed datasets randomly generated by the binomial distribution. Then the same analysis method as that for the primary study endpoint will be used to obtain the comparison results between the two groups in each imputed dataset. Finally, Rubin's Rule will be used to pool these results. If there is a pair of assumed response rate that overturns the study conclusion, that is, p value is more than 0.05, the two assumed response rates will be the cut-off points.

Subgroup analysis will be performed on the primary efficacy endpoint (the proportion of subjects whose IGA score is 0-1 and decreased by ≥ 2 points from baseline at W16) and the key secondary efficacy endpoint (the proportion of subjects achieving EASI-75 at W16) by gender (male/female), severity of baseline disease (moderate [IGA = 3]/severe [IGA = 4]), history of allergic diseases or allergy history (yes/no), baseline EASI ($<$ baseline median EASI/ \geq baseline median EASI), baseline PP-NRS ($<$ baseline median PP-NRS/ \geq baseline median PP-NRS). The analytical method is the same as the primary analysis method for the

primary efficacy endpoint and the key secondary efficacy endpoint. The subjects with missing subgroup variables will not be included.

Sensitivity analysis will be performed on the primary efficacy endpoint (the proportion of subjects whose IGA score is 0-1 and decreased by ≥ 2 points from baseline at W16) and the key secondary efficacy endpoint (the proportion of subjects achieving EASI-75 at W16) using the stratification during randomization and the method the same as the main estimator.

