7.4.3. Analysis of the primary efficacy endpoint and key secondary efficacy endpoints

Label of estimand	Description of estimand	Main estimator			Sensitivity/ Supplementary analysis
		Analysis sets	Rules for imputation	Model/method for the main analytical methods	
Estimand of primary endpoint	
The difference in efficacy in patients aged 12 years and older with moderate to severe AD and weighing > 40 kg between the CBP-201 300 mg Q2W group and placebo group.
 
A patient is considered as treatment success if the patient has an IGA score of 0-1 which is decreased by ≥ 2 points from baseline at W16.
 
A patient should be regarded as treatment failure if he/she uses prohibited drugs/treatments specified in the protocol for which the study treatment must be early terminated or other rescue therapy that has a major impact on the assessment of the primary endpoint due to poor treatment effect, or has early termination of treatment/EOT due to adverse events.
	FAS (will include all subjects in RS1 who have received the study drug at least once).	
For subjects who experience intercurrent events, their visits after the intercurrent events will be handled in accordance with the strategies for managing intercurrent events listed in Table 7.4.2.
 
If the target variable is still missing after application of the strategies for managing intercurrent events, the multiple imputation (MI) method will be used to impute the missing data in the placebo group, and the J2R (jump to reference) method will be used to impute the missing data in the CBP- 201 group.
	
Differences in response rates between the treatment group and placebo group and their 95% confidence intervals will be analyzed using the Cochran-Mantel-Haenszel test stratified by baseline disease severity (IGA 3 or 4). The Type I error level for statistical significance of the difference in response rates between CBP-201 and placebo is set at 0.05 (two-sided test).
	
Sensitivity analysis 1: When the target variable is still missing after application of the strategy for managing intercurrent events, it will be classified as treatment failure.
 
Sensitivity analysis 2: When the target variable is still missing after application of the strategy for managing intercurrent events, tipping point analysis will be used for analysis.
 
Sensitivity analysis 3: For the subjects who are incorrectly stratified and randomized, the analysis will be performed using correct stratification factors and the same method as the main estimand;
 
Supplementary analysis 1: Primary analysis will be performed using the PPS.
 
Supplementary analysis 2: The treatment policy strategy will be used for all intercurrent events; the FAS will be used, and the missing data will be subject to the imputation rules of the main estimator, that is, the multiple imputation method (MI) will be used to impute the missing data in the placebo group, and the J2R (jump to reference) method will be used to impute the missing data in the CBP-201 group.

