
Label of estimand	Description of estimand	Main estimator			Sensitivity/ Supplementary analysis
		Analysis sets	Rules for imputation	Model/method for the main analytical methods	
					reference) method will be used to impute the missing data in the test group.
Estimand of key secondary endpoints	
The differences in the following measures in patients aged 12 years and older with moderate to severe AD and weighing ≥ 40 kg between the CBP-201 300mg Q2W group and the placebo group:
 
 • The proportion of subjects achieving EASI-75 at W16 • The proportion of subjects whose weekly average PP-NRS is decreased by ≥ 4 points from baseline at W16; • The proportion of subjects whose weekly average PP-NRS is decreased by ≥ 3 points from baseline at W16; • Change and percentage change in the weekly average PP-NRS from baseline at W16; • The proportion of subjects 	FAS (will include all subjects in RS1 who have received the study drug at least once).	
For subjects who experience intercurrent events, their visits after the intercurrent events will be handled in accordance with the strategies for managing intercurrent events listed in Table 7.4.2. If the target variable is still missing after application of the strategies for managing intercurrent events, the multiple imputation (MI) method will be used to impute the missing data in the placebo group, and the J2R (jump to reference) method will be used to impute the missing data in the CBP- 201 group.
	
For categorical variables, differences in response rates between the treatment group and placebo group and their 95% confidence intervals will be analyzed using the Cochran-Mantel-Haenszel test stratified by baseline disease severity (IGA 3 or 4).
 
For continuous variables, analysis will be performed using an MMRM model that will include treatment group, baseline disease severity (IGA 3 or 4), baseline value of the corresponding endpoint, visit, interaction of visit and treatment group, and the LSMEAN estimate values and their 95%
	
Sensitivity analysis 1: When the target variable is still missing after application of the strategy for managing intercurrent events, categorical variables will be classified as treatment failure. Continuous variables should be imputed with WOCF.
 
Sensitivity analysis 2: For the subjects who are incorrectly stratified and randomized, the analysis will be performed using a correct stratification factor and the method the same as the main estimator;
 
Supplementary analysis 1: Primary analysis will be performed using the PPS.
 
Supplementary analysis 2: The treatment policy strategy will be used for all intercurrent events; the FAS will be used, and the missing data will be subject to the imputation rules of the main estimator, that is, the multiple imputation method (MI) will be used to impute the missing data in the placebo group, and the J2R (jump to reference) method will be used to impute the

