Tipping point analysis: To evaluate the robustness of the primary efficacy endpoint analysis, tipping point analysis should be performed on the primary efficacy endpoint at W16. The tipping point method is binary, that is, the assumptions of missing values of the active treatment group and the placebo group are mutually independent. Assuming that the response rate of missing values of the two groups increases by 10% from 0 to 100%, the subjects with a missing response in the two groups at a certain percentage will be randomly assigned as responders and non-responders in 30 imputed datasets randomly generated by the binomial distribution. Then the same analysis method as that for the primary study endpoint will be used to obtain the comparison results between the two groups in each imputed dataset. Finally, Rubin's Rule will be used to pool these results. If there is a pair of assumed response rate that overturns the study conclusion, that is, p value is more than 0.05, the two assumed response rates will be the cut-off points.

Subgroup analysis will be performed on the primary efficacy endpoint (the proportion of subjects whose IGA score is 0-1 and decreased by ≥ 2 points from baseline at W16) and the key secondary efficacy endpoint (the proportion of subjects achieving EASI-75 at W16) by gender (male/female), severity of baseline disease (moderate [IGA = 3]/severe [IGA = 4]), history of allergic diseases or allergy history (yes/no), baseline EASI ($<$ baseline median EASI/ \geq baseline median EASI), baseline PP-NRS ($<$ baseline median PP-NRS/ \geq baseline median PP-NRS). The analytical method is the same as the primary analysis method for the primary efficacy endpoint and the key secondary efficacy endpoint. The subjects with missing

subgroup variables will not be included to analysis.

Sensitivity analysis will be performed on the primary efficacy endpoint (the proportion of subjects whose IGA score is 0-1 and decreased by ≥ 2 points from baseline at W16) and the key secondary efficacy endpoint (the proportion of subjects achieving EASI-75 at W16) using the correct stratification factor and the method the same as the main estimator.

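### Does the reversed sensitivity analysis for mis-stratified subjects leave the primary CMH stratification open?

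*SAP*

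**What the plan says.** The current SAP, section 7.4.3, analyses the primary endpoint with a "Cochran-Mantel-Haenszel test stratified by baseline disease severity (IGA 3 or 4"). The wording is the same in Protocol Table 12.4 and in SAP Version 1.0 (20 September 2022). None of the three says whether a mis-stratified subject is placed by the stratum used at randomisation or by the IGA actually recorded at baseline. The same factor enters the MMRM for the continuous key secondary endpoints and the imputation model, where it is called the "stratification factor (severity of baseline disease").

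The sensitivity analyses do address mis-stratification, and the two SAP versions take opposite sides:

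| Place in 7.4.3 | SAP Version 1.0 | Current SAP |
|---|---|---|
| Primary endpoint, Sensitivity analysis 3 | "the analysis will be performed using correct stratification factors and the same method as the main estimand" | "the analysis will be performed using the stratification during randomization and the same method as the main estimand" |
| Key secondary endpoints, Sensitivity analysis 2 | "the analysis will be performed using a correct stratification factor and the method the same as the main estimator" | "the analysis will be performed using the stratification during randomization and the method the same as the main estimator" |
| Closing paragraph (IGA response and EASI-75) | "using the correct stratification factor and the method the same as the main estimator" | "using the stratification during randomization and the method the same as the main estimator" |

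Section 6 of both versions lists incorrect stratified randomisation among the Stage 1 deviations that affect efficacy analysis, without a count. Section 7.1 of both versions defines the efficacy baseline as the most recent value available ahead of Stage 1 randomisation.

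**The concern.** A sensitivity analysis is normally the alternative to the main one. Read that way, Version 1.0 implies a main CMH on strata as randomised, and the current SAP implies a main CMH on corrected strata, while the sentence describing the main test did not change.

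Timing adds to the worry. The current SAP reports a meeting of 18 October 2023 as past. Protocol 6.3.2 planned to unblind and analyse the Stage 1 data of the 255 subjects once they had finished Stage 1. If the stratum rule was changed after arms were known, the confirmatory test would no longer be fully pre-specified, and someone could in principle choose the version with the smaller p-value. Mis-stratification did occur in this trial, so the question is not hypothetical.

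**Working it through.** **1. Can the current SAP be read only one way?** Three statements bear on it:

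- the main CMH is stratified by baseline disease severity (7.4.3);
- baseline for efficacy is the last pre-randomisation value (7.1);
- the alternative analysis uses the stratum from randomisation (7.4.3).

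Together they give actual baseline IGA as the main stratum and the randomisation stratum as the sensitivity analysis. No statement in the current SAP conflicts with this.

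**2. The plan's own figures, which do not depend on the stratum rule.** Inputs from Protocol 12.3: 144 and 72 completers, 27% v 9%, two-sided 0.05, 15% dropout.

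- Pooled rate: (144 × 0.27 + 72 × 0.09) / 216 = 45.36 / 216 = 0.21.
- Null SE: √[0.21 × 0.79 × (1/144 + 1/72)] = 0.0588.
- Alternative SE: √[0.27 × 0.73/144 + 0.09 × 0.91/72] = 0.0501.
- Power: Φ[(0.18 − 1.96 × 0.0588) / 0.0501] = Φ(1.29) = 90.2%, against the stated 90%.
- Sample size: 216 / 0.85 = 254.1, with whole subjects in a 2:1 ratio 255, as planned.
- The same formula at 28.1% v 10.7% gives 85.9%, against the stated figure of more than 85%.

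**3. How much does the stratum rule matter?** The documents do not give the number mis-stratified, the IGA 3/4 split or the response by stratum, so these are assumptions. Two simulations were run with 255 subjects, 2:1 allocation within the recorded stratum and half the subjects in each IGA stratum. Each trial was analysed by CMH with recorded strata and with true strata.

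- Simulation A: 20,000 trials per setting; response by stratum 36%/18% active and 13%/5% placebo (averages 27% and 9%).
- Simulation B: 6,000 trials per setting; 37%/17% and 14%/4% (also 27% and 9%).

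Trials in which the two CMH tests disagree on significance:

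| Mis-stratified | 27% v 9% | 20% v 9% |
|---|---|---|
| A: 1% | 0.25% | 0.85% |
| A: 2% | 0.44% | 1.42% |
| A: 5% | 0.68% | 2.20% |
| A: 10% | 0.98% | 2.88% |
| B: 3 of 255 (1.2%) | 0.43% | 1.50% |
| B: 10 of 255 (3.9%) | 0.62% | 2.43% |
| B: 25 of 255 (9.8%) | 1.10% | 4.13% |

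- Power with about 10% mis-stratified, 27% v 9%: 95.4% with strata as randomised and 95.6% (A) or 95.7% (B) with true strata. At 20% v 9% (B): 64.0% v 64.7%.
- Type I error in A: 0.046-0.050 as randomised and 0.047-0.052 corrected (Monte Carlo SE about 0.0015). In B: 0.043-0.052 and 0.046-0.054 (SE about √(0.05 × 0.95/6000) = 0.003).
- If someone always took the smaller p-value (A): 0.0477, 0.0504, 0.0540 and 0.0533, against 0.0464, 0.0488, 0.0499 and 0.0492 with strata as randomised. That adds 0.1 to 0.4 points.

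**4. What will the report contain?** Under either version, one stratification is the main analysis and the other is the sensitivity analysis. Supplementary analysis 1 on PPS1 also leaves out subjects with incorrect stratification. All these results are planned.

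**The case for a change.** The strongest reply is that Version 1.0 had the same baseline definition. If that definition means actual IGA, Version 1.0 planned a sensitivity analysis identical to its main analysis. It is more natural to suppose that Version 1.0 meant strata as randomised and that the later text moved the main test. The three matching edits do not look like a typing slip.

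Part of this stands: the current text does not name the stratum, the implied main analysis differs between versions, and the later wording probably follows the planned unblinding. The rest goes further than the documents allow.

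- The three edits are one drafting choice repeated, and Version 1.0's wording may itself have been the slip.
- No unblinding date is given. The front pages of the current SAP are not in the reviewed text, so a dated reason for the change may exist. Section 7.8 lists departures from the protocol, not from Version 1.0, so its silence shows nothing.
- The current SAP keeps 30 imputations for the primary analysis, as Version 1.0 had, which suggests that the primary analysis was carried forward.
- Difference from a superseded version is not in itself an error.

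Requiring strata as randomised would reverse what the current SAP implies and would itself be a late change. Strata as randomised follow the allocation; actual IGA describes the patient. Both are fixed before treatment, so choosing between them is a fair trade-off.

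A related worry is that the deviations behind PPS1 were settled again in October 2023. That meeting is described as blinded, the listed causes are essentially those of Version 1.0, only Supplementary analysis 1 is touched, and nothing shows that any subject changed status.

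**Conclusion.** No change to the plan follows. The observation about the text is accurate, but it is a missing detail that the current SAP's baseline definition and its sensitivity analysis fill in one consistent way. Following the plan as written gives a valid test. Under the assumptions above, type I error stays near 0.05 with either stratum, power at the design effect moves by 0.3 points or less, and the two tests disagree in about 1% of trials or fewer at 27% v 9%. The largest figure, about 4%, needs both a smaller effect (20% v 9%) and nearly 10% mis-stratified. Any such disagreement would show, because both analyses are planned. The increase of 0.1 to 0.4 points in type I error arises only from picking the better result, which neither version permits.

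These sizes rest on an assumed count of mis-stratified subjects and assumed response rates by stratum. Naming the stratum in the footnote of the primary results table is ordinary reporting and needs no amendment.
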